**If the 3M Clear Aligners are not able to be seated and/or do not fit, contact 3M clinical study monitor.**

#### 5.2.5 Treatment with 3M Clear Aligners

After placement of the 3M Clear Aligners:

- Instruct subject on how to insert and remove the 3M Clear Aligners. Make sure subject is able to insert and remove 3M Clear Aligners before they leave the office. Investigator may provide auxiliaries to help subject with comfort while wearing 3M Clear Aligners and help with removal of the 3M Clear Aligners.
- Review and discuss the Patient Care and Use Instruction Sheet with subject.
- Allow each subject adequate time to ask questions.

- Provide subject with a 3M Clear Aligner case box.
- Inform the subject to return all 3M Clear Aligners in the original packaging along with the white box.
- In the event that a 3M Clear Aligner is lost or damaged, instruct subject to contact the office immediately.
- If a 3M Clear Aligner is lost or breaks within less than 7 days, instruct subject to begin wearing the previous set of 3M Clear Aligners.
- If a 3M Clear Aligner is lost or breaks after 7 days or more, instruct subject to begin wearing the next set of 3M Clear Aligners.
- Site will return all used and damaged 3M Clear Aligners to study 3M.
- Use shipping labels provided by 3M.
- Return 3M Clear Aligners in packaging provided and complete required packaging documentation.

**If a 3M Clear Aligner is broken or lost, site should contact 3M clinical study monitor for replacement.**

#### 5.2.6 Mid-Course Correction or Refinement

In the event of a mid-course treatment correction or refinement, the following procedures should be followed:

- Generate digital scan of subject's teeth.
- Go to the Ordering Page in Treatment Management Portal and select option 6 to indicate that further treatment stages are cancelled.
- Submit new Treatment Management Portal order.
- After notification, review and approve both new target and stage set-ups.
- Corrected treatment will continue with 3M Clear Aligners identified as Tray # 1.

## 6. Subject Compliance

Routine office visits will be used to encourage subject compliance to study protocol. A 3M representative will monitor sites to oversee study documentation and compliance with study protocol.

## 7. Assessment of Efficacy

Efficacy of the 3M Clear Aligners for each subject will be based on the assessment by the investigator that teeth correction is progressing as expected at each orthodontic visit, and that the subject's teeth have reached the final target set-up by the end of treatment.

## 8. Assessment of Safety

### 8.1 Safety Parameters

The primary measures of safety will be evaluated by the incidence of adverse events reported during the study.

### 8.2 Adverse Events

The Investigator is responsible for identifying adverse events that occur to each subject throughout the study and follow-up period. An adverse event can occur at any time during the conduct of the study, in any phase of the study or after the study is completed. An adverse event can be identified by the Investigator or reported by the subject.

Note: The Federal Privacy Rule (HIPAA) specifically permits the use and disclosure of protected health information “without written authorization of the individual” when used for public health activities such as reporting adverse events, tracking FDA-related products, enabling recalls, repairs, replacements, lookbacks, or conducting post-market surveillance [45 CFR 164.512]. This use and disclosure is subject to the *minimum necessary* standard, i.e. “the minimum necessary to accomplish the intended use, disclosure, or request” [45 CFR 164.502(b)(1)].

#### Definitions

- Adverse event (AE) means any undesirable clinical occurrence in a subject whether or not it is considered to be device or drug related.
- Device-related adverse event (adverse device effect) is an AE considered by the Investigator to have a reasonable likelihood of being associated with the treatment device.
- Serious adverse device effect is a device effect that has a serious adverse effect on health or safety causing hospitalization or prolonged hospitalization, or is life threatening or causes death.
- Adverse drug experience is an AE that is considered by the Investigator to have a reasonable likelihood of being associated with the treatment drug.
- Serious adverse drug experience is an adverse drug experience that is fatal or life-threatening, requires inpatient hospitalization or prolongation of existing hospitalization, a persistent or significant disability/incapacity, or results in a congenital anomaly/birth defect.
- An Unanticipated Adverse Device Effect (UADE) means any serious adverse effect on health or safety or any life-threatening problem or death caused by or associated with a

3M Confidential

Document Name: CLIN-PROT-ICH-US-05-300635

Clinical and Non-Clinical: CLIN-INDEX-3M-SPON-US-05-013821, Clinical and Non-Clinical: CLIN-INDEX-3M-SPON-US-11-050005

device, if that effect, problem or death was not previously identified in nature, severity or degree of incidence in the Protocol or application (including a supplementary plan or application), or any other unanticipated serious problem associated with a device that relates to the rights, safety, or welfare of subjects.

All adverse events will be followed until they are resolved or for 30 days after the subject's participation in the study ends.

## Recording and Reporting

The Investigator records each material-related adverse event on an Adverse Device Effect Record. Documentation includes the description, severity, seriousness, date of onset and resolution, relationship to the treatment material, action taken and outcome.

The Investigator must promptly report an adverse device effect to the 3M study monitor. If the adverse device effect is also considered by the Investigator to be serious and/or unanticipated, the Investigator must report it to the IRB as soon as possible and within IRB requirements.

A serious AE involving a non-3M commercialized product is reported to the 3M study monitor and IRB of record.

If a subject has no adverse device effect during the study, the absence of such must be recorded on the CRF.

## 9. Statistics

The primary efficacy dataset will include all subjects enrolled who have worn at least one set or first stage of 3M Clear Aligners in the study. The primary dataset will be referred to as the full analysis set or FAS.

A secondary efficacy dataset will be defined as the per protocol or PP dataset. This PP dataset will exclude subjects with major protocol deviations that will affect efficacy assessment of the 3M Clear Aligners. The major deviations that will lead to exclusion from the PP dataset will be fully documented and justified in the Statistical Analysis Plan (SAP) and/or pre-lock data meeting minutes. Two major protocol deviations that will lead to PP exclusion include significant non-compliance with aligner wear and not completing treatment due to non-treatment-related reasons (e.g. unexpectedly moving out of state). In general, a subject's failure to complete treatment due to strongly anchored teeth will be considered a treatment failure.

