### 3.7.2 Subject Discontinuation

The Investigator may discontinue individual subjects from the study at any time. Subjects may voluntarily withdraw from the study at any time. The Investigator will provide a written report on the appropriate CRF describing the reason for discontinuance and the date of discontinuance.

A subject will be discontinued from the study if any of the following occur:

- Subject fails to comply with instructions for wearing the 3M Clear Aligner as indicated per the Investigator treatment plan, for the duration required.
- Subject fails to show up at scheduled visits. Attempts will be made to schedule subjects and if they are not responsive, they may be discontinued.
- Subject elects to terminate participation in the study.
- Investigator elects to withdraw the subject (with written justifications about safety, noncompliance or for other safety reasons).
- Subject experiences a severe adverse reaction to the 3M Clear Aligner.
- Subject requires dental work that cannot wait until the end of the study.

Subjects who are withdrawn after wearing aligners will not be replaced. If possible, any procedures or assessments planned for the subject on withdrawal from the study should be performed when intention to withdraw the subject is announced

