#### 5.2.4 Attachments

Based upon the investigator treatment plan, composite based attachments may be placed on the subject's teeth by the investigator using the 3M Attachment Template. Attachments are used to assist the 3M Clear Aligners in certain tooth movements or to engage the 3M Clear Aligners to directly apply pressure to certain teeth depending on the tooth size, shape and angulation.

3M Confidential

Document Name: CLIN-PROT-ICH-US-05-300635

Clinical and Non-Clinical: CLIN-INDEX-3M-SPON-US-05-013821, Clinical and Non-Clinical: CLIN-INDEX-3M-SPON-US-11-050005

Investigators may also place buttons they currently use in practice on the subjects teeth to assist with creating tooth movements and correcting occlusion in conjunction with attachments. Investigators may use buttons with elastics to assist in creating tooth movements such as rotation, intrusion, extrusion, translation. Investigators will bond the buttons onto the subjects' teeth according to the manufacturer's instructions. The investigator may modify the 3M Clear Aligner as needed, so that the 3M Clear Aligners fit around the buttons on the teeth.

Instructions for placing 3M attachments using the 3M Attachment Template can be found in the Aligner Attachment instructions for use. Instructions will cover the following:

- Tooth preparation
- Acid Etching
- Priming Teeth
- Bond the attachments and light cure
- Inspect the 3M Clear Aligners for any defects.
- Seat the 3M Clear Aligners to assess fit and adjust as needed.
- Assess the removal of the 3M Clear Aligners and adjust as needed.

For bonding buttons, follow the manufacturer instructions for use.

- Bond the buttons and modify the 3M Clear Aligners as needed to fit around the buttons.
- Inspect the 3M Clear Aligners for any defects.
- Seat the 3M Clear Aligners to assess fit and adjust as needed.
- Assess the removal of the 3M Clear Aligners and adjust as needed.

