### 9.1.2 Analysis of Primary Endpoint

The primary endpoint is the proportion of subjects achieving treatment success or attainment of teeth movements targets of the final set-up. It is possible for the final set-up to be modified mid-treatment or to be refined at the end of treatment, and thus success of the aligner will be based on the last or most relevant final set-up. Primary endpoint will be ascertained at the end of active 3M Clear Aligner wear (before retainer use). Subjects missing their primary endpoint assessment (e.g., subjects lost to follow-up) will be assumed to be treatment failures. The two-sided 95% confidence interval of this proportion will be computed using the Wilson score method. Documentation of subjects excluded from either the FAS or PP datasets for the computation of success rate will be justified and documented prior to datalock.

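### The primary denominator leaves out subjects whose first aligners could never be seated, so a device or planning failure is dropped instead of counted

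*Combined protocol and SAP*

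**What the plan says.** - **Primary analysis set (Section 9).** The FAS is "all subjects enrolled who have worn at least one set or first stage of 3M Clear Aligners in the study". No minimum wear time is given.
- **Missing endpoints (Section 9.1.2).** "Subjects missing their primary endpoint assessment (e.g., subjects lost to follow-up) will be assumed to be treatment failures".
- **Exclusions (Section 9.1.2).** "Documentation of subjects excluded from either the FAS or PP datasets for the computation of success rate will be justified and documented prior to datalock".
- **Interval (Section 9.1.2).** "The two-sided 95% confidence interval of this proportion will be computed using the Wilson score method".
- **Sequence (Section 5.1.2).** Consent, scan and treatment plan belong to the initial visit. The sponsor then makes the aligners and ships them ahead of the next six-week visit.
- **Fit (Sections 5.2.4 and 5.2.5).** The attachment steps include "Seat the 3M Clear Aligners to assess fit and adjust as needed". The bold line before Section 5.2.5 reads "If the 3M Clear Aligners are not able to be seated and/or do not fit, contact 3M clinical study monitor". Neither place says how a subject whose aligners never seat is classified in the analysis.
- **Replacement (Section 3.7.2).** "Subjects who are withdrawn after wearing aligners will not be replaced". Nothing is said about withdrawal before wear.
- **All enrolled subjects (Section 9.1.1).** They are used for demographic summaries. No success rate is planned for them.

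**The concern.** A treated-only analysis set in a single-arm study is unobjectionable when the reason for not starting has nothing to do with the product. Here the product is an appliance built from the subject's own scan and plan. If it cannot be seated, that is a result of the device or of the planning. The protocol already reasons this way in one case: Section 9 treats non-completion caused by strongly anchored teeth as, in general, a treatment failure. Failure to seat has no matching rule, and the wear condition removes such a subject by default.

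At stake is the one number that carries the primary result. There is no comparator and no formal test (Sections 3.3 and 9.3), so the success proportion and its interval are what readers will use. A proportion that conditions on the device having been worn answers a narrower question than whether enrolled subjects who were supplied with aligners were corrected.

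**Working it through.** **The plan's own figure.** The only figure to reproduce is the enrolment cap in Section 1.5: 12 sites × 15 subjects = 180, which agrees with Section 9.2. The plan states no expected success rate, interval width, dropout rate or fit-failure rate.

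**Does any rule catch the never-seated subject?**

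1. The subject is enrolled at the initial visit, before aligners exist (Section 5.1.2).
2. Fitting of the first set is attempted and does not succeed, and the subject leaves without wearing a set.
3. The FAS condition of having worn a set is not met, so the subject is not in the primary denominator.
4. The missing-as-failure rule works on the denominator of the success rate, so it does not bring the subject back.
5. No other planned success rate includes the subject, because the per-protocol set is narrower still.

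**Direction and size.** Let N be the number enrolled, k the number who never wore a set because it could not be seated or did not fit, and s the number of successes.

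- FAS rate: p = s/(N − k)
- Rate with the k counted as failures: s/N
- Gap: s/(N − k) − s/N = p × k/N, which is positive whenever k ≥ 1 and s ≥ 1

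*Assumptions, not from the documents:* all 180 places are filled, success among wearers is about 80%, and k is 0, 2, 5, 9 or 18.

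| k | FAS rate | k counted as failures | Gap (points) |
|---|---|---|---|
| 0 | 144/180 = 80.0% | 144/180 = 80.0% | 0.0 |
| 2 | 142/178 = 79.8% | 142/180 = 78.9% | 0.9 |
| 5 | 140/175 = 80.0% | 140/180 = 77.8% | 2.2 |
| 9 | 137/171 = 80.1% | 137/180 = 76.1% | 4.0 |
| 18 | 130/162 = 80.2% | 130/180 = 72.2% | 8.0 |

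At k = 9 the two-sided 95% Wilson interval moves from 73.5–85.4% (FAS) to 69.4–81.8%.

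**Sensitivity to the assumed success rate.** With 60% to 90% success among wearers, the gap is 0.7–1.0 points (k = 2), 1.7–2.5 (k = 5), 3.0–4.5 (k = 9) and 6.0–9.0 (k = 18).

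**Effect of replacement.** If the FAS were refilled to 180, the gap would be p × k/(180 + k). For k = 9 this is 144/180 − 144/189 = 80.0% − 76.2% = 3.8 points, against 4.0 without replacement.

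**The case against.** The strongest case on the other side is that the sequence may never happen. A poor fit can be adjusted at the chair, and aligners that still do not seat lead to a call to the monitor, not to withdrawal. Fit failure is not among the discontinuation reasons listed in Section 3.7.2. A subject whose aligners are adjusted or remade and then worn enters the FAS, and counts as a failure if later lost. Leaving out people who drop out while aligners are being made is also reasonable. All of this stands. It limits the point to subjects who are never successfully fitted, and it means k may be zero. It does not supply a rule for such a subject if one occurs.

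Three stronger readings are tempting, and the documents do not support them.

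- **That every seating problem removes a subject from the denominator.** The provisions for adjustment and monitor contact say otherwise. Only never wearing a set does so.
- **That never-seated subjects will be replaced and the bias made worse.** Section 3.7.2 bars replacement after wear and is silent before it. Permission is an inference from silence, and replacement hardly changes the gap in any case.
- **That Section 9.1.2 lets the sponsor remove FAS members once outcomes are known.** The sentence imposes a duty to justify and document exclusions before data lock. Its natural reading covers enrolled subjects who never wore a set. It does not say that a subject who meets the definition may be taken out, though it does not rule this out in words.

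The absence of a performance goal or test also limits the consequence: no pass/fail decision turns on a few points.

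**Conclusion.** The point holds in a limited form. By its stated definition, the FAS drops an enrolled subject whose delivered aligners could never be seated or worn, and the missing-as-failure rule cannot bring that subject back. The effect on the success rate can only be upward. Its size cannot be found from the documents: it is nil if no such subject occurs, about 2 points for 5 of 180, about 4 points for 9 and about 8 points for 18, at roughly 80% success among wearers. The upper end requires one enrolled subject in ten never to wear a set because of fit, and nothing in the documents indicates that frequency. The calculation also assumes that each of these subjects is properly a failure, which is apt for device-related non-wear but not for people who left for unrelated reasons before any fitting. This is an inexpensive improvement to the definition. It does not show that the planned estimate is wrong.

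**What to change.** In Section 9:

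1. Define the primary denominator as every enrolled subject for whom fitting of the first set was attempted.
2. Count as failures those who never wore a set because it could not be seated or did not fit.
3. Leave out only subjects who withdrew before any fitting attempt, and report their number and reasons.
4. Add a sensitivity success rate, with its Wilson interval, on all enrolled subjects.

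In Section 9.1.2, keep the duty to justify and document exclusions, including those from the FAS, since it supports item 3. Add a clause that no subject who meets the FAS definition may be removed.

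The cost is a few sentences, possibly a slightly less favourable success rate, and a record of the outcome of the first fitting attempt. The case report forms are not among the documents, and the accountability records listed in Section 3.8 cover receipt, use and return but not a failed fitting, so this item may have to be added. How non-fitting aligners are managed clinically is outside this point.

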### 9.1 Statistical Methods

#### 9.1.1 Analysis of Baseline and Demographic Characteristics

Subject demographics (age, gender) will be summarized for all enrolled subjects and for those considered evaluable for the primary endpoint. Individual subject malocclusions diagnosed at baseline or study enrollment will be summarized also.

### 9.1.2 Analysis of Primary Endpoint

The primary endpoint is the proportion of subjects achieving treatment success or attainment of teeth movements targets of the final set-up. It is possible for the final set-up to be modified mid-treatment or to be refined at the end of treatment, and thus success of the aligner will be based on the last or most relevant final set-up. Primary endpoint will be ascertained at the end of active 3M Clear Aligner wear (before retainer use). Subjects missing their primary endpoint assessment (e.g., subjects lost to follow-up) will be assumed to be treatment failures. The two-sided 95% confidence interval of this proportion will be computed using the Wilson score method. Documentation of subjects excluded from either the FAS or PP datasets for the computation of success rate will be justified and documented prior to datalock.

### 9.1.3 Analysis of Secondary endpoints

In general, the reported summary statistics for continuous measures will include number, mean, standard deviation, median and range. Reported summary statistics for categorical measures will include number and frequency.

Summaries of the overall percent completion or accuracy per subject will be summarized overall and for those categorized under treatment success or failure. Percent completion or percent accuracy will involve comparison of the final tooth positions relative to the planned or targeted positions against pre-treatment or baseline positions.

In addition, individual teeth movement and the malocclusions resolved in this study will be summarized as appropriate.

The secondary endpoints of treatment compliance, percent comfort and percent satisfaction will be summarized for various performance parameters.

Furthermore, summaries of attachment use, button use, and possible bond failures will be presented. In addition, occurrence of mid-course corrections and refinements will be summarized.

## 9.2 Sample Size Justification

The sample size for the study will be up to 180 subjects. The sample size was based on historical subject compliance and understanding of alignment procedures.

## 9.3 Interim analyses and Criteria for the Termination of the Study

At least one interim case study summary analysis may be conducted to examine the data regarding efficacy, safety and protocol deviations. A decision to stop the study may follow the interim summary analysis based on clinical results.

Given that no formal statistical testing will occur in this study, no allowance for alpha spending will be needed with any interim analysis.

## **10. Monitoring**

3M, as sponsor of this study, is responsible for ensuring the proper conduct of the study with regard to protocol adherence and validity of the data recorded on the CRFs. 3M has therefore assigned a study monitor to this study. The monitor will be responsible for securing the compliance of the Principal Investigators to the signed agreement, the study Protocol and all applicable FDA regulations, guidelines and standards. The specific plans for monitoring will be detailed in the Monitoring Plan.

The assigned study monitor will conduct regular monitoring visits to the study site for which he/she is responsible. The Principal Investigator will allow the study monitor to inspect all Case Report Forms and the subject's clinic records and/or original medical records at these visits. These visits are for the purpose of verifying adherence to the Protocol and the completeness and accuracy of the data being entered on the Case Report Forms. The Investigator must make available the following for inspection and copying, in addition to any other documents deemed necessary for the integrity of the study data:

- Informed consent forms and HIPAA forms
- Protocol amendments, IRB/EC approval
- Protocol deviations
- Facilities at the study site
- Accounting of all 3M Clear Aligners
- Adverse events/adverse device effects that have been documented and reported

The progress of the study will be monitored by:

- Periodic on-site review
- Telephone communications
- Review of CRFs and source documents (e.g. patient hospital records, clinical charts, progress/doctor's notes, lab test results, x-rays, etc.)

Note: The Federal Privacy rule (HIPAA) specifically permits the use and disclosure of protected health information "to a person subject to the jurisdiction of the Food and Drug Administration (FDA) [e.g. study sponsor] with respect to an FDA-related product or activity for which that

person has responsibility, for the purpose of activities related to the quality, safety, or effectiveness of such FDA-regulated product or activity” [45 CFR 164.512(b)(1)(iii)].

